9.2 Setting

Eligibility criteria for study inclusion are:

- 1) Aged of 65 years or older as of the study start
- 2) Have a known residency within the specific country at start of study period (1 October 2023)
- 3) Have received four or five Covid-19 vaccine doses (of AZD1222, BNT162b2, or mRNA-1273 vaccines only [AZD1222 as part of the primary vaccination course only; an original/bivalent BA.4-5/BA.1 mRNA vaccine as the fourth/fifth vaccine dose] prior to start of study period
- 4) No history of Covid-19 hospitalization prior to start of study period

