9.3 Variables

Exposures

The Nordic countries implemented national vaccination campaigns against SARS-CoV-2 from December 27, 2020, providing free vaccinations to all residents. Phased distribution plans were implemented prioritizing vaccination of individuals at highest risk of Covid-19 complications (nursing home residents, healthcare workers, and individuals of older age). Denmark almost exclusively used

mRNA vaccines after full or partial discontinuation of AZD1222 in March 2021 due to serious but rare events of thrombosis with thrombocytopenia. The AZD1222 was similarly halted in Finland and Sweden for the younger population but continued as part of the utilized primary course schedules for the population aged 65 years or more. The mRNA vaccines have been predominantly used in all countries for seasonal dose/additional Covid-19 vaccine vaccinations. Ad26.COVS has seen very limited use. The three Nordic countries have vaccinated around 6 times more individuals with BNT162b2 than with mRNA-1273. Prioritized fourth dose vaccination rollouts to the vulnerable elderly and those living in nursing home facilities were initiated in spring 2022 in Finland and Sweden, and has been offered more broadly to the general population since summer 2022. During autumn and winter 2022-23, the bivalent BA.4-5 and BA.1 mRNA-seasonal vaccines were mainly given as a fourth dose in Denmark and as a fourth or fifth dose in Finland and Sweden. Vaccination with the monovalent XBB.1.5-containing Covid-19 mRNA vaccines mainly as a fifth or a sixth dose was initiated from 1 October 2023 in the three countries.

Outcomes

Covid-19 hospitalization will be defined as first inpatient hospitalization with a registered Covid-19-related diagnosis and a positive PCR test for SARS-CoV-2 (within 14 days before to 2 days after the day of admission). We will define Covid-19 death as death within 30 days of a positive PCR test for SARS-CoV-2. In the table below, we provide further country-specific details.

Outcome variable	Country	Data source and details
Covid-19 hospitalization	Denmark	The National Patient Register and the Danish Microbiology Database. Defined as a hospitalization with a PCR positive test for SARS-CoV-2 within 14 days before to 2 days after the admission date, b) inpatient contact or at least 12 hours of contact, and c) a Covid-19 relevant diagnosis code (ICD-10: B342, B342A, B948A, B972, B972A, B972B, B972B1, Z038PA1)

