9.7 Data analysis

Procedures

We will use a matched study design to evaluate the effectiveness of receiving a monovalent XBB.1.5-containing Covid-19 vaccine in comparison with not receiving a Covid-19 vaccine during the autumn and winter 2023-24. Individuals who during the study period receive an XBB.1.5-containing Covid-19 vaccine as either a fifth or sixth dose will be matched on the day of vaccination with individuals who have not yet received a fifth or sixth dose, respectively. Individuals will be matched on age (5-year bins), calendar time of last mutual vaccine dose (i.e., either 4th dose for the 5 vs 4- or 5th dose for the 6 vs 5-matched pairs), sex, region of residence, vaccination priority groups (i.e., individuals at high-risk of severe Covid-19), number of selected comorbidities (0, 1, 2, ≥ 3 of chronic pulmonary disease, cardiovascular conditions, diabetes, autoimmunity-related conditions, cancer, and moderate to severe renal disease). The day the XBB.1.5-containing Covid-19 vaccine was administered within each matched pair will serve as the index date for both individuals. If individuals who were included as a matched XBB.1.5-containing vaccine-unvaccinated individual (i.e., a reference individual) receive an XBB.1.5-containing vaccine later than the assigned index date, they will be allowed to potentially re-

enter as an XBB.1.5-containing vaccine recipient in a new matched pair on that given date and the follow-up for the current pair will be censored.

We will follow individuals from one week after the index date (to ensure full immunization among XBB.1.5-containing Covid-19 vaccine recipients) up until the day of an outcome event, end of week 18 (end of week 24 if possible) since the index date, receipt of additional Covid-19 vaccine dose, death, emigration, or end of the study period, whichever occurs first. The date of vaccination is denoted as the index date. The start of the follow-up period will commence on Day 0, corresponding to eight days after the index date. The figure below illustrates the study cohort construction, as an example of the comparison fifth vs fourth dose.

Statistical analysis

We will use 1:1 exact matching without replacement with the prespecified covariates to find a precise pairing of individuals receiving a monovalent XBB.1.5-containing Covid-19 vaccine to individuals not receiving a Covid-19 vaccine.

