9.8 Supplementary analyses and quality control

Quality control will be conducted indirectly to evaluate the validity of our main analyses by 1) making sure that the prevalence of the different schedules and the number of study endpoints match national surveillance dashboards and reports, 2) descriptive and analytical results are compatible with our previous findings, and 3) using a Common Data Model (CDM), by which national register data are standardized to a common structure, format and terminology in order to allow the same statistical programming scripts to be used in each country. The use of a CDM with common statistical programming scripts will facilitate efficient use of resources and reproducibility of the statistical analyses. We will ensure the scientific quality of the work, by division of review tasks (including statistical code review) and responsibilities in a timely fashion and by adhering to the ENCePP Code of Conduct (see attachment). We will perform matching quality diagnostics to assess the control of matched parameters. We will include a sensitivity analysis where we start follow-up after 3 weeks (21 days) after the index date to further reduce the potential of transient healthy vaccinee effect around the time of vaccination as well as *spill-over effect* (that is, prior to the index date) given that some severe Covid-19 events may take longer time to develop.

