9.9 Limitations of the research methods

The study has a number of limitations. Given the observational nature of the study, confounding is a potential major concern. Thus, we will consider key predictors of the outcomes or proxies hereof. The

accuracy of our exposure, Covid-19 vaccination, will rely on the registered vaccination within the registers and recorded time of administration. To the best of our knowledge, the assignment of the type of the XBB.1.5-containing Covid-19 vaccine was unselective and our study period reflects a time when the XBB.1.5-containing Covid-19 vaccines was offered to the to the general population aged 65 years or older as fifth and sixth Covid-19 vaccine dose.

Our outcome definitions will most likely also capture a small proportion of cases where the infection with SARS-CoV-2 only partly contributed to or coincided with the timing of the hospitalization or death. Also, we cannot certify that we will capture all Covid-19 related hospitalizations and deaths within each country. SARS-CoV-2 was ascertained by positive PCR test results and we have no information on at-home antigen testing for SARS-CoV-2. Thus, those who acquired SARS-CoV-2 infection and were hospitalized or died but were not PCR tested will be missed. Our active comparative design, however, mitigates concerns that such outcome misclassification will differ between compared groups to any larger extent as e.g., opposed to comparisons with individuals never vaccinated with the Covid-19 vaccines. Any misclassification will likely tend to skew estimates toward conservative results if differences truly existed.

Both vaccination status and SARS-CoV-2 variants of predominance are strongly correlated with calendar time. This reduces the possibilities for a valid direct comparison between effectiveness estimates obtained during different periods of variant predominance (background transmission rates and population characteristics most likely differ) as well as evaluating longer-term follow-up effectiveness in relation to only one SARS-CoV-2 variant. As such, the analyses will instead reflect evaluations of the initiated Covid-19 vaccination strategies at that given time. In Denmark, Covid-19 hospitalizations peaked on 1 December 2023, when the JN.1 subvariant was predominating.

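### Eligibility is fixed at 1 October 2023 and the PCR windows are not limited to samples after the index date, so infections confirmed before time zero can count as outcomes, chiefly as early Covid-19 deaths

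*Protocol*

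**What the plan says.** **Eligibility.** Age, residency, prior doses and Covid-19 hospitalization history are all judged at the start of the study period (Protocol 9.2, and the target trial table in 9.1). The history criterion reads "No history of Covid-19 hospitalization prior to start of study period".

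**Time zero.** Section 9.7 sets it later: "The day the XBB.1.5-containing Covid-19 vaccine was administered within each matched pair will serve as the index date for both individuals". Vaccinees are "matched on the day of vaccination with individuals who have not yet received a fifth or sixth dose, respectively". The matching variables in 9.3 and 9.7 are age, sex, region, timing of the last shared dose, risk group and comorbidity count. None concerns recent infection or current admission.

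**Follow-up.** It starts eight days after the index date (9.1 and 9.7; 9.7 also says one week).

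**Outcomes (9.3).** "Covid-19 hospitalization will be defined as first inpatient hospitalization with a registered Covid-19-related diagnosis", with a positive PCR from 14 days before to 2 days after admission. "We will define Covid-19 death as death within 30 days of a positive PCR test for SARS-CoV-2". Neither definition requires the sample to be dated after the index date.

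**Safeguard (9.8).** "We will include a sensitivity analysis where we start follow-up after 3 weeks (21 days) after the index date". The stated reasons are a healthy-vaccinee effect and spill-over from before the index date.

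**The concern.** A target trial applies its entry criteria at assignment. Here assignment falls on any vaccination day from October 2023 onward, while entry criteria are frozen at 1 October. The interval between them can include much of the winter wave: section 9.9 says "In Denmark, Covid-19 hospitalizations peaked on 1 December 2023, when the JN.1 subvariant was predominating".

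Someone with a positive test shortly before the index date therefore stays eligible. If that person dies or is admitted soon after day 8, the event is counted although the infection preceded the vaccination being evaluated. Such events carry no information on VE. If they are unequally spread between the arms, they bias it.

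The exposed results are those nearest the index date: the week-6 VE and the first point in the waning regression, especially for Covid-19 death, which has the longer window and its own block in the example results table (section 12).

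**Working it through.** The protocol gives no figure of its own here, so there is nothing to reproduce.

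**1. Date arithmetic (index date = day 0).** Earliest qualifying PCR = start of follow-up minus window length.

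| Start of follow-up | Admission (14 days) | Death (30 days) |
|---|---|---|
| Day 8 (primary) | 8 - 14 = -6 | 8 - 30 = -22 |
| Day 21 (sensitivity) | 21 - 14 = +7 | 21 - 30 = -9 |

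If one week means day 7, the first row becomes -7 and -23. In the primary analysis, events on days 8-13 (admission, 6 days) and days 8-29 (death, 22 days) can rest on a pre-index test.

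**2. Share of events with a pre-index test, f.** Assumptions, none from the protocol: constant incidence and a stated PCR-to-event lag L. Then f is the mean of P(L > t) over the event days t. Section 9.7 defines the first interval as follow-up days 0-42 with follow-up Day 0 at index day 8, which gives index days 8-50 (43 days). Eighteen weeks give index days 8-134 (127 days).

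- *Death, truncated exponential.* P(L > t) = (exp(-t/m) - exp(-30/m)) / (1 - exp(-30/m)), and zero from day 30. For m = 6, 8, 10, 12 days, f = 3.6%, 5.8%, 7.6%, 9.1% in the first interval; with whole-day lags, 3.0%, 5.1%, 6.8%, 8.3%. So about 3-9%. Over 18 weeks, about 1-3%.
- *Death, uniform on 0-30 days.* P(L > t) = (30 - t)/31. The sum over t = 8 to 29 is (22 + 21 + ... + 1)/31 = 253/31 = 8.16. Then 8.16/43 = 19% and 8.16/127 = 6%.
- *Hospitalization.* 0.3% (exponential shape, scale 3 days) to 3.3% (uniform 0-14) in the first interval; 0.1-1.1% over 18 weeks.
- *Death, day-21 start, 43-day interval.* 0.2-1.0% (exponential) or 3.4% (uniform).

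Section 9.7 also counts the end of follow-up from the index date. If the first interval ended at index day 42, the exponential range for death would be about 4-11%.

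**3. Effect on VE.** Let f be the share among reference-arm events, RR the true risk ratio, and d the proportionate deficit of pre-index infections among vaccinees (d = 0: same as references; d = 1: none). Then

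RR_obs = (1 - f) x RR + f x (1 - d).

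VE is inflated only if d exceeds the true VE; below that it is diluted. For death with f = 0.09 and a true VE of 50%:

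- d = 0: 0.91 x 0.5 + 0.09 = 0.545, so VE reads 45.5%
- d = 0.5: 0.455 + 0.045 = 0.500, so VE reads 50%
- d = 1: 0.455 + 0 = 0.455, so VE reads 54.5%

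Over 18 weeks with f = 0.03, the same VE reads 48.5% to 51.5%. For hospitalization with f = 0.033 and a VE of 55.4% (one of the figures cited in section 7), it reads 53.6% to 56.9%.

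**4. Waning slope.** Only the first interval is affected, since every window has closed by index day 30. In an equally weighted regression, the first of three points has slope weight (1 - 2)/2 = -0.5, and the first of four has (1 - 2.5)/5 = -0.3. An error of +4.5 points in the first VE (d = 1) shifts the slope by -2.25 or -1.35 percentage points per 6 weeks. An error of -4.5 points (d = 0) shifts it by the same amount upward. The actual weights will follow precision.

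**The case against.** **The authors anticipated this.** Section 9.8 names both mechanisms and plans a day-21 start. For hospitalization that closes the gap completely. For death it narrows the window from 22 days to 9, with a residual of about 1% or less under the exponential lags. This stands, and it limits the point. The day-21 analysis is only a sensitivity analysis, however, and neither it nor the primary analysis is free of the problem for death.

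**Direction.** A reader might infer that these events fall almost only on references, so that VE is inflated and waning is spurious. Infected people do tend to put off vaccination, so upward bias is the likelier sign. The protocol gives no split by arm, though, and inflation requires d to exceed the true VE. Reading 50% as 55% is the extreme case d = 1, not an estimate.

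**The hospitalization criterion.** A reader might also blame the history criterion alone. It concerns earlier admission, not infection. Moving it to the index date would leave in people who had tested positive but had not been admitted, and both windows would stay open. Because only a first admission counts, someone admitted between 1 October and the index date would, on the natural reading, add event-free time for hospitalization. If such people are mostly references, that lowers VE. They could still count as Covid-19 deaths.

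**Constant incidence.** While incidence is rising, the share would be smaller than shown; while it is falling, larger. The protocol does not give the distribution of index dates.

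**Conclusion.** The defect holds on the protocol's own dates: eligibility precedes assignment, no infection or admission check is stated at assignment, and tests up to 6 days (admission) or 22 days (death) before the index date can qualify an event.

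Its size rests on assumed lags and constant incidence. It could be material for Covid-19 death at week 6 and for the waning slope: at the upper exponential share, an error of up to about 4.5 points either way on a VE of 50%, and about twice that under a uniform lag (0.19 x 0.5 = 9.5 points). It is small for hospitalization and for 18-week VE. The sign is probably upward but is not established, and the case for correcting it does not depend on the sign. This should be fixed; it does not undermine the hospitalization results or the 18-week estimates.

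**What to change.** 1. In sections 9.1, 9.2 and 9.7, apply these conditions on the index date to both pair members: no earlier Covid-19 hospitalization, not currently an inpatient with Covid-19, and no positive SARS-CoV-2 PCR in the preceding 30 days. Re-apply them when a reference re-enters as a vaccinee.
2. In section 9.3, count an admission or death only if its qualifying positive sample is dated after the index date. A cut-off at day 8 is not needed for this problem: it would also discard infections on days 0-7, which follow time zero.
3. Keep the day-21 analysis for the healthy-vaccinee effect.

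Step 2 brings the event-days that can rest on a pre-index test to zero for both outcomes; moving the history criterion alone would not.

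The cost is a few lines in the common script, using PCR and admission dates the study already links, and a small loss of potential pairs.

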9.3 Variables

Exposures

The Nordic countries implemented national vaccination campaigns against SARS-CoV-2 from December 27, 2020, providing free vaccinations to all residents. Phased distribution plans were implemented prioritizing vaccination of individuals at highest risk of Covid-19 complications (nursing home residents, healthcare workers, and individuals of older age). Denmark almost exclusively used

mRNA vaccines after full or partial discontinuation of AZD1222 in March 2021 due to serious but rare events of thrombosis with thrombocytopenia. The AZD1222 was similarly halted in Finland and Sweden for the younger population but continued as part of the utilized primary course schedules for the population aged 65 years or more. The mRNA vaccines have been predominantly used in all countries for seasonal dose/additional Covid-19 vaccine vaccinations. Ad26.COVS has seen very limited use. The three Nordic countries have vaccinated around 6 times more individuals with BNT162b2 than with mRNA-1273. Prioritized fourth dose vaccination rollouts to the vulnerable elderly and those living in nursing home facilities were initiated in spring 2022 in Finland and Sweden, and has been offered more broadly to the general population since summer 2022. During autumn and winter 2022-23, the bivalent BA.4-5 and BA.1 mRNA-seasonal vaccines were mainly given as a fourth dose in Denmark and as a fourth or fifth dose in Finland and Sweden. Vaccination with the monovalent XBB.1.5-containing Covid-19 mRNA vaccines mainly as a fifth or a sixth dose was initiated from 1 October 2023 in the three countries.

Outcomes

Covid-19 hospitalization will be defined as first inpatient hospitalization with a registered Covid-19-related diagnosis and a positive PCR test for SARS-CoV-2 (within 14 days before to 2 days after the day of admission). We will define Covid-19 death as death within 30 days of a positive PCR test for SARS-CoV-2. In the table below, we provide further country-specific details.

Outcome variable	Country	Data source and details
Covid-19 hospitalization	Denmark	The National Patient Register and the Danish Microbiology Database. Defined as a hospitalization with a PCR positive test for SARS-CoV-2 within 14 days before to 2 days after the admission date, b) inpatient contact or at least 12 hours of contact, and c) a Covid-19 relevant diagnosis code (ICD-10: B342, B342A, B948A, B972, B972A, B972B, B972B1, Z038PA1)
	Finland	National Care Register for Health Care and the National Infectious Diseases Register. Defined as a hospitalization with a PCR positive test for SARS-CoV-2 within 14 days before to 2 days after the admission date, b) inpatient hospital contact, and c) a Covid-19 relevant main diagnosis (ICD-10: J00-J22, J46, J80-J84, J851, J86, U071, U072).
	Sweden	The Swedish Patient Register and the Register on surveillance of notifiable communicable diseases (SmiNet). Defined as a hospitalization with a PCR positive test for SARS-CoV-2 within 14 days before to 2 days after the admission date, b) inpatient contact or at least 12 hours of contact, and c) a Covid-19 relevant diagnosis code (ICD-10: U071, U072, U109)
Covid-19 death	Denmark	The Civil Registration System and the Danish Microbiology Database. Defined as (the date of) death within 30 days after PCR positive test for SARS-CoV-2.
	Finland	The Finnish Population Information System and the National Infectious Diseases Register. Defined as (the date of) death within 30 days after PCR positive test for SARS-CoV-2.

	Sweden	The Total Population Register, the Cause of Death Register, and the Swedish Patient Register and the Register on surveillance of notifiable communicable diseases (SmiNet). Defined as (the date of) death within 30 days after PCR positive test for SARS-CoV-2.
--	--------	--

Covariates

We will take the following potential confounders into account by matching: age (using birth cohort), sex, region of residency, calendar time of last mutual vaccine dose (i.e., either 4th dose for the 5 vs 4- or 5th dose for the 6 vs 5-matched pairs), Covid-19 risk groups (nursing home residents, at risk of severe Covid-19 due to comorbidities), and selected comorbidities. Further country-specific details of covariate definitions are provided in table below.

Variable	Country	Data source and details	Values/codes
Age	Denmark	The Civil Registration System. Recorded birth year. Age defined as the country-specific start date minus birth year.	Categorical (for adjustment, using birth year): 5-year bins Binary (for stratification): $</\geq$ 75 years
	Finland	The Finnish Population Information System. Recorded birth year. Age defined as the country-specific start date minus birth year.	
	Sweden	The Total Population Register. Recorded birth year. Age defined as the country-specific start date minus birth year.	

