	Finland	Care register for Health Care and Special Reimbursement Register. Defined as primary or secondary diagnoses registered within 2 years prior to the start of the study period.	Binary: yes/no (ICD-10 codes: C00–C43, C45–C80, C97, D05.1, D39)
	Sweden	National Patient Register. Defined as any recorded ICD-10 diagnosis during inpatient or outpatient contact and before first Covid-19 vaccination (look-back 3 years).	Binary: yes/no (ICD-10 codes: C00–C96 (without C44), D45–D47)
Comorbidity 6: Moderate to severe renal disease	Denmark	The National Patient Register. Defined as primary diagnoses regardless of type of hospital contact registered before the start date for the country-specific rollout of the fourth vaccine dose (look-back 3 years).	Binary: yes/no (ICD-10 codes: I12, I13, N00–N05, N07, N11, N14, N17–N19, Q61)
	Finland	Care register for Health Care. Defined as primary or secondary diagnoses prior to the start of the study period.	Binary: yes/no (ICD-10 codes: I12, I13, N00–N05, N07, N08, N11, N14, N18, N19, E102, E112, E142)
	Sweden	National Patient Register. Defined as any recorded ICD-10 diagnosis during inpatient or outpatient contact and before first Covid-19 vaccination (look-back 3 years).	Binary: yes/no (ICD-10 codes: I12, I13, N00–N05, N07, N11, N14, N17–N19, Q61)
Influenza vaccination status for season 2023–2024	Denmark	The Danish Vaccination Register. Defined according to the date of influenza vaccine and XBB.1.5-containing vaccine vaccinations.	Categorical (for subgroup analysis only ^d): co-administered on the same date; received influenza vaccine within 1 weeks before to 1 week after XBB.1.5-containing vaccine dose administration but no on same date; no influenza vaccine administered within 1 weeks before to 1 week after of XBB.1.5-containing vaccine dose administration.
	Finland	The National Vaccination Register. Defined according to the date of influenza vaccine (VaxigripTetra or InfluxacTetra) and XBB.1.5-containing vaccine vaccinations.	
	Sweden	The National Vaccination Register. Defined according to the date of influenza vaccine and XBB.1.5-containing vaccine vaccinations.	

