We expect the majority of the study population will receive both the influenza and the XBB.1.5-containing Covid-19 vaccine on the same day, meaning that the statistical power of the subgroup analyses within populations not concurrently vaccinated will likely be lower.

Given the broad inclusion within each Nordic country, our results will likely have a high degree of generalizability to other similar populations. However, our assessment of the comparative effectiveness of monovalent XBB.1.5-containing Covid-19 mRNA-vaccines given as a fifth or sixth dose against severe Covid-19 outcomes may only indirectly support any evaluation of the effectiveness of these vaccines within other Covid-19 vaccination schedule scenarios. Our findings may similarly not directly generalize to certain subpopulations not individually studied or to populations with a

demographically different composition. Such subpopulations include for example the general population younger than 65 years old or other specific clinical subgroups that were not studied.

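### Finland's Covid-19 hospitalization code list admits PCR-positive admissions coded to influenza, which may tilt the influenza co-administration contrast

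*Protocol*

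**What the plan says.** Protocol section 9.3 (Outcomes) gives one general definition for all three countries: "first inpatient hospitalization with a registered Covid-19-related diagnosis and a positive PCR test for SARS-CoV-2". The country table then sets the details. All three rows share the PCR condition, worded for Finland as "Defined as a hospitalization with a PCR positive test for SARS-CoV-2 within 14 days before to 2 days after the admission date". The diagnosis condition differs:

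- Finland: an inpatient contact and "c) a Covid-19 relevant main diagnosis (ICD-10: J00-J22, J46, J80-J84, J851, J86, U071, U072".
- Sweden: "c) a Covid-19 relevant diagnosis code (ICD-10: U071, U072, U109".
- Denmark: "ICD-10: B342, B342A, B948A, B972, B972A, B972B, B972B1, Z038PA1".

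Only the Finnish row contains J codes, and only the Finnish row is limited to the main diagnosis.

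Influenza vaccination status appears in the covariate table of section 9.3 as "for subgroup analysis only". The footnote to that row carries a stray negative, but the matching list in section 9.7 omits influenza vaccination in any case. Section 9.7 defines the influenza subgroups by the status of the XBB.1.5 recipient. Section 9.9 adds: "We expect the majority of the study population will receive both the influenza and the XBB.1.5-containing Covid-19 vaccine on the same day".

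**The concern.** In ICD-10, J09-J11 is the influenza block, and it lies inside J00-J22. An admission whose main diagnosis is influenza is not, on its face, one with a Covid-19-related diagnosis as the general definition requires. The footnote in section 9.3 that defends country-specific codes speaks of comorbidity codes, so it does not explain the outcome list.

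The code list matters because exposure is tied to influenza vaccination. Suppose some Finnish events are influenza admissions in patients who also test positive for SARS-CoV-2. Influenza vaccine then lowers the number of such events among recipients vaccinated against both on the same day, but not among recipients without influenza vaccine. Objective 3 asks how co-administration affects XBB.1.5 effectiveness. Part of any difference seen in Finland could reflect influenza vaccine preventing influenza rather than a change in what the XBB.1.5 vaccine does.

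**Working it through.** **Step 1: trace one patient through the rules.** Take an inpatient with a positive PCR five days before admission, main diagnosis J10 and no other listed code. The Finnish row counts this patient. The Swedish and Danish rows do not, because neither lists a J code.

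**Step 2: inputs.** The protocol gives no figure for this point, so there is none to reproduce.

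- f: share of reference-arm Finnish events that are PCR positive and coded to influenza. Not given; varied at 2% and 5%.
- u: effectiveness of influenza vaccine against these events. Assumed 30-50%.
- p0: influenza-vaccine coverage among references. Assumed 20-40%.
- w: XBB.1.5 effectiveness against being SARS-CoV-2 positive. From 0 up to the 54% against symptomatic infection cited in section 7. It enters because every counted event still needs a positive PCR.
- f, w and p0 are taken as equal in the two subgroups, with no true co-administration effect.

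**Step 3: spurious gap for objective 3.** Relative to references, the risk ratio for influenza-coded events is

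- same-day subgroup: (1 − w)(1 − u)/(1 − p0·u)
- subgroup without influenza vaccine: (1 − w)/(1 − p0·u)

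The remaining events have the same risk ratio in both subgroups and cancel, so

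gap in VE = f(1 − w)·u/(1 − p0·u).

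The factor u/(1 − p0·u) runs from 0.30/(1 − 0.06) = 0.319 to 0.50/(1 − 0.20) = 0.625.

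| f | w = 0 | w = 0.54 |
|---|---|---|
| 2% | 0.64 to 1.25 points | 0.29 to 0.58 points |
| 5% | 1.60 to 3.13 points | 0.73 to 1.44 points |

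Under these assumptions the gap is positive whenever f and u exceed 0 and w is below 1, so it makes co-administration look better than it is.

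**Step 4: what shrinks it.** Section 9.7 defines the third subgroup by no influenza vaccine within one week either side of the XBB.1.5 dose, not by none all season. If a fraction q of it is influenza-vaccinated at other times, with the same protection, the gap is multiplied by (1 − q). At q = 0.5 (an assumption) it halves. Pooling dilutes it again: at an assumed one-third weight for Finland, the full ranges become about 0.29/3 = 0.1 to 1.25/3 = 0.4 points (f = 2%) and 0.73/3 = 0.2 to 3.13/3 = 1.0 points (f = 5%).

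**Step 5: overall Finnish effectiveness.** Let V be effectiveness against Covid-19 hospitalization, using the 55.4%, 70.7% and 76% cited in section 7. Let d be the difference in influenza-vaccine coverage between arms (assumed 0.3 or 1.0), with u set at 30% or 60% and w at 0 or 54%. Admitting the influenza-coded events changes the overall VE by

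f[(1 − V) − (1 − w)(1 − u·d)].

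At f = 5% the extremes are

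- 0.05 × [0.24 − 1 × (1 − 0.09)] = −3.35 points
- 0.05 × [0.446 − 0.46 × (1 − 0.60)] = +1.31 points

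The change is positive in 7 of the 24 input combinations. In the other 17 these events dilute the estimate.

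**The case against.** The strongest reply is that the PCR condition already does most of the work. A reader might infer from the code range that Finland counts influenza admissions as such. It does not: the same table cell requires a positive SARS-CoV-2 PCR and an inpatient contact. If the PCR condition were ignored, an f of 20-40% with influenza vaccine effectiveness of 30-60% and a coverage difference of 1 would give 0.2 × 0.3 = 6 to 0.4 × 0.6 = 24 points, but the protocol does not define the outcome that way. Only co-positive, influenza-coded admissions are at issue, and section 9.9 partly concedes coincidental infection: "Our outcome definitions will most likely also capture a small proportion of cases where the infection with SARS-CoV-2 only partly contributed to or coincided". That limits the size. It does not remove the point, because section 9.9 mentions neither influenza nor the Finnish range. Its expectation that misclassification makes results conservative also does not cover a contrast in which the mechanism can create a difference where none exists.

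A reader might also infer that influenza-vaccine protection inflates the overall XBB.1.5 estimate. Step 5 shows that the sign is not fixed, so the document does not support that.

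Finally, it is tempting to ask Finland to adopt the Swedish rule with U codes in any position. That would add admissions with a secondary Covid-19 code, some of them incidental, and drop PCR-positive pneumonia coded only to a respiratory main diagnosis. It would still not match the Danish list. It is a trade of sensitivity against specificity, not a correction that the document compels.

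**Conclusion.** The point holds in a narrow form. Finland alone lets PCR-positive admissions with an influenza main diagnosis count as Covid-19 hospitalizations, which does not fit the general definition, and no reason is given. These events may favour the same-day subgroup over the subgroup without influenza vaccine. Taking both values of w together, the Finnish gap is about 0.3 to 1.25 points at f = 2% and 0.7 to 3.1 points at f = 5%. It is smaller if some of the third subgroup were influenza-vaccinated outside the one-week window, and smaller again in the pooled estimate.

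The direction for objective 3 rests on f, w and reference coverage being equal across the subgroups. The size rests on f, which the protocol does not give, and on assumed influenza vaccine effectiveness and coverage. No direction can be claimed for overall Finnish effectiveness. The Danish and Swedish estimates are not affected. Nor is Covid-19 death, which uses no diagnosis codes.

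**What to change.** In the Finnish row of the outcome table in section 9.3, exclude J09-J11 from the main-diagnosis list. Add a Finland-only sensitivity analysis of Covid-19 hospitalization restricted to U071/U072, reported for the overall estimate and for the influenza subgroups.

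The exclusion removes this route by which influenza-vaccine protection reaches the outcome, while PCR-positive pneumonia under the other J codes is kept. The sensitivity analysis shows how far the Finnish result depends on the remaining respiratory codes.

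The cost is one edit to a code list and one further run of the common R scripts. A few PCR-positive admissions with an influenza main code in which Covid-19 did contribute would be lost.
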